Behavioral Treatment of Menopausal Insomnia; Sleep, Depression, Daytime (MENO)

NCT01933295

Updated on April 19th 2017

Insomnia is a key symptom of the menopausal transition with 40-50% of postmenopausal women (> 17 million) having insomnia. Insomnia associated with menopause has a pattern of sleep disturbance predominantly characterized by sleep maintenance difficulties including frequent awakenings and arousals, reduced sleep efficiency, and overall fragmented sleep. It has recently been demonstrated that this pattern of sleep disturbance, difficulty maintaining sleep, increases throughout the progression of menopause. We have recently found sleep maintenance problems in menopause are associated with reduced work performance, increased healthcare utilization, and impaired quality of life.

Cognitive-behavioral therapy for insomnia (CBT-I) yields equivalent short-term efficacy and superior long-term durability to pharmacological treatment of insomnia. However, the efficacy of cognitive behavioral therapy for insomnia comorbid with menopause, one of the primary focuses of the present proposal, has not been tested. Traditional CBT-I has disadvantages however, including the need for a trained therapist and significant time commitment on the part of the patient. Therefore, widespread availability of multicomponent CBT-I is limited by the relatively low number of CBT sleep specialists, complexity of therapy, and patient burden. Thus, another aim of this project is to test the acute and long-term efficacy of a single component behavioral therapy for menopausal-related insomnia. Given the significant daytime impairment present in insomnia comorbid with menopause including depression, quality of life, and fatigue, a final aim of this proposal is to determine the efficacy of CBT-I on these measures in women with menopausal-related insomnia.

Each patient who meets the criteria and opts for CBT-I as part of their standard clinical treatment for insomnia will be asked if they wish to participate in the study. Consented subjects will then receive CBT-I treatment for 4 weeks (2 face-to-face sessions and 2 phone contacts). The patients will maintain a sleep diary to measure sleep efficiency (number of hours asleep over number of hours in bed) and sleep latency (amount of time taken to fall asleep). This diary will be collected at each visit. The patients will fill out the following pre and post standardized surveys before and after the start of treatment: ISI, BAI, ESS, FSI, BDI-II, and SF-36 QoL, PSAS, DBAS. These surveys will measure secondary factors, such as, severity of insomnia, sleepiness, hyperarousal, fatigue, anxiety, depression, and quality of life (all included in the appendix). Our primary aim is to maximize and/or improve sleep efficieny in patients (number of hours asleep over number of hours in bed) and to shorten sleep latency (amount of taken to fall asleep). Other secondary measures will be taken regarding aspects other than sleep in patients. These will be recorded through the surveys mentioned above and will measure improvement in severity of insomnia, sleepiness, depression, anxiety, dysfunctional beliefs and quality of life.

Each variable of interest (sleep diary measures and questionnaire assessments) will be compared between pre and post-treatment (the primary evaluation time points) using standard analysis of covariance, with the baseline demographics as covariates. Then the data on sleep efficiency, sleep latency, will be analyzed across all of the weekly time points using repeated measures analysis of covariance, with covariates included for the baseline levels of those variables along with age, BMI, and time since cancer development. The repeated measures modeling will primarily evaluate the main time effect. The repeated measures sphericity will be examined and an appropriate variance/covariance modeling structure will be used. If the analysis of variance assumption of distributional normality is violated, then an appropriate data transformation will be utilized.

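### The stated aims include efficacy of CBT-I and of a single-component therapy, short and long term, but the methods describe one uncontrolled CBT-I group with no assessment after post-treatment

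*Combined protocol and SAP*

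**What the plan says.** The document is short and its sections are unnumbered. The background and aims text states three efficacy aims:

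1. CBT-I for insomnia accompanying menopause. It refers to "the efficacy of cognitive behavioral therapy for insomnia comorbid with menopause, one of the primary focuses of the present proposal".
2. A simpler therapy. It says that "another aim of this project is to test the acute and long-term efficacy of a single component behavioral therapy for menopausal-related insomnia".
3. Daytime outcomes (depression, quality of life, fatigue). It says that "a final aim of this proposal is to determine the efficacy of CBT-I on these measures in women with menopausal-related insomnia".

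The procedures paragraph defines who enters: "Each patient who meets the criteria and opts for CBT-I as part of their standard clinical treatment" is invited to take part. It then says: "Consented subjects will then receive CBT-I treatment for 4 weeks (2 face-to-face sessions and 2 phone contacts"). Diaries are kept during treatment, and questionnaires are completed before and after.

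The analysis paragraph says that each diary and questionnaire measure "will be compared between pre and post-treatment (the primary evaluation time points"). Sleep efficiency and latency are then modelled over the weekly points, and "The repeated measures modeling will primarily evaluate the main time effect". The covariates are the baseline levels of those variables "along with age, BMI, and time since cancer development".

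**The concern.** The aims and the methods do not describe the same study. The aims call for an estimate of what two treatments achieve, one of them over the long term. The methods deliver one treatment, in patients who chose it, followed to the end of a 4-week course.

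If the trial is run as the methods say, the single-component aim gets no data. The two CBT-I aims get a before-after change that does not support a claim of efficacy. If the aims are what the investigators intend, this document holds no methods or analysis that would meet them. In either case a reader cannot judge the eventual conclusions against a plan fixed in advance.

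**Working it through.** No sample size, power or effect figure is stated, so there is no figure to reproduce. The check sets each aim against what the procedures and analysis paragraphs provide.

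**What the methods provide**

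- Treatments given: 1 (CBT-I, to all consented patients).
- Single-component groups: 0.
- Comparators or allocation: 0.
- Time points named: pre, post and weekly. The only duration given is 4 weeks.
- Assessments described after post-treatment: 0.
- Model terms: time and baseline covariates, with no group term and no group-by-time term.

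**Aim by aim**

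| Aim | Treatment given? | Comparator? | What the data would show |
|---|---|---|---|
| 1. CBT-I, insomnia | Yes | No | Uncontrolled change over time |
| 2. Single component, acute and long-term | No | No | Nothing |
| 3. CBT-I, daytime measures | Yes | No | Uncontrolled pre/post change |

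The counts are 0 of 3 aims with a comparator, 2 of 3 with uncontrolled change only, and 1 of 3 with no data.

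**Why the time effect is not an efficacy estimate**

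With one treated group, the mean change from pre to post is a sum:

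change = effect of CBT-I + natural course + expectation + regression to the mean

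Only the sum can be estimated. Age, BMI and baseline level are fixed for each woman. Adjusting for them may sharpen the estimate of the sum but cannot separate its parts, because no untreated or otherwise-treated women supply the other terms. The regression term depends on how women are selected. It could be zero if entry does not depend on the baseline sleep measure. The entry criteria are not shown, so this cannot be settled.

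**Signs of where the mismatch comes from**

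The analysis adjusts for time since cancer, yet the background describes no cancer population. The procedures and analysis paragraphs never mention menopause or a single-component therapy. This suggests, without proving, that the methods were not written for these aims.

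**The case against.** Single-arm before-after studies are legitimate, and the methods describe one openly. The background promises no randomisation and no control group. It gives the limited availability of multicomponent CBT-I as the reason for studying a simpler therapy, and does not say the two will be compared. The procedures paragraph also states its own primary aim, to improve sleep efficiency and shorten sleep latency, which fits its own methods. On this view the real defects are one aim without methods and one word, efficacy, that is too strong. The cancer covariate would then be a separate slip.

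Much of this is fair. A single arm is not in itself an error, and the document does not show that a parallel-group trial was ever intended. The threats to a before-after change are generic and cannot be sized here. None of this removes the contradiction: an aim is stated for which no treatment is given, and efficacy is claimed from a contrast that cannot isolate it.

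Three readings that might rescue the text do not succeed:

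- **The CBT-I given is itself the single-component therapy.** The text does not say so, and the background introduces that therapy as an answer to the drawbacks of traditional multicomponent CBT-I. Even on this reading, the comparator and the long-term assessment are still missing.
- **Calling pre and post the primary time points implies later ones.** The only others named are the weekly diary points. No end is stated for these, but no follow-up visit is described.
- **The missing material lies elsewhere.** The entry criteria and the appendix are not shown. The appendix is described as holding the questionnaires, and neither would be expected to supply a treatment group.

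**Conclusion.** The concern holds, and the plan should not stand as written. Followed exactly, it gives no data on the single-component therapy, acute or long-term, and only uncontrolled change for the two CBT-I aims. None of the three efficacy aims has a comparator.

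These are counts of what the text describes. They assume that the unseen entry criteria and appendix contain no second group and no later assessment. No size is put on the bias in the before-after change. Which part is wrong, the aims or the methods, cannot be decided from the document; the cancer covariate makes the methods a plausible candidate.

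**What to change.** Reconcile the aims with the procedures and analysis. There are two routes.

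**If the methods describe the intended study:**

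- Delete the single-component aim, including its long-term part.
- Restate the two CBT-I aims, and the conclusion they lead to, as within-woman change during CBT-I rather than efficacy.
- Correct or justify the covariate for time since cancer.

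This costs wording only, though the claim becomes weaker.

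**If the aims describe the intended study:**

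- Replace the methods with those that belong to it: the groups, how women are assigned to them, and the times of the post-treatment and long-term assessments.
- Make a comparison between groups the main analysis, in place of the time effect.

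This means rewriting the procedures and analysis paragraphs. If women have already been treated only as those paragraphs now describe, the first route is the only one open for their data.

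### As worded, the pre/post comparison ignores that both values come from the same woman; for the eight questionnaires it is the only analysis, so power is lost if within-woman correlation is positive

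*Combined protocol and SAP*

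**What the plan says.** The document's sections are unnumbered. The statistical analysis paragraph opens with "Each variable of interest (sleep diary measures and questionnaire assessments") and says these "will be compared between pre and post-treatment (the primary evaluation time points) using standard analysis of covariance, with the baseline demographics as covariates". That sentence covers diary measures and questionnaires alike.

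The next sentence changes method: "Then the data on sleep efficiency, sleep latency, will be analyzed across all of the weekly time points using repeated measures analysis of covariance". Only in that model does the plan adjust for a woman's starting value of the outcome, alongside other patient characteristics. Within-woman covariance comes up only after that: "The repeated measures sphericity will be examined and an appropriate variance/covariance modeling structure will be used".

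The procedures paragraph describes one treatment given to everyone who consents, and says of the questionnaires: "The patients will fill out the following pre and post standardized surveys before and after the start of treatment". Eight are listed: ISI, BAI, ESS, FSI, BDI-II, SF-36, PSAS and DBAS. The background also mentions "a single component behavioral therapy for menopausal-related insomnia", but the pre and post values are paired within a woman however many arms there are.

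**The concern.** Comparing pre with post makes time the factor in the model, so each woman supplies two observations. A standard analysis of covariance with only demographics as covariates has a single residual error term and assumes those observations are independent. The plan uses a different name, adds baseline outcome levels and mentions a covariance structure only for the weekly analysis of two diary variables.

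If the sentence is followed as written, the error term for the pre/post difference contains between-woman variation that pairing would remove. Sleep efficiency and sleep latency are partly protected by the weekly model, although the plan calls pre and post the primary evaluation points, so their main comparison has the same wording. The questionnaires have no second analysis, and they carry the depression, fatigue and quality-of-life results that the background sets out as the final aim. A null result there could not be told apart from lost precision.

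**Working it through.** The documents give no sample size, significance level, power, SD or correlation, so there is no stated figure to reproduce. What follows is an illustration under assumptions.

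**Assumed inputs.** n women with complete pairs; equal SD (set to 1) at both times; within-woman correlation rho; two-sided 5% test; true change set so that a paired analysis has 80% power.

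**Do the demographics restore the pairing?** No. A woman's baseline demographics are the same in both of her rows, so with complete pairs they are orthogonal to time. The estimated pre/post difference does not change. They remove only the between-woman variance that they explain.

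**Standard errors.**
- True SE of the mean change: sqrt(2(1 - rho)/n).
- SE if the rows are treated as independent: sqrt(2/n).
- Ratio: k = 1/sqrt(1 - rho).

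**Closed form.** With the effect at 1.96 + 0.84 = 2.80 true SEs:
- actual size = 2[1 - Φ(1.96k)]
- power = Φ(2.80 - 1.96k)

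For rho = 0.5, k = 1.414 and 1.96k = 2.772. Size is 0.0056 and power is Φ(0.028), about 51%.

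**Simulation.** Stacked least squares with time and two demographics that explain no variance (2n - 4 df) against a paired t-test; 40,000 replicates at n = 20 and 40, and 20,000 at n = 80.

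| rho | k | Size, closed form | Size, simulated n = 40 | Power, closed form | Power, simulated n = 40 |
|---|---|---|---|---|---|
| -0.2 | 0.91 | 7.4% | 7.0% | 84% | 85% |
| 0 | 1.00 | 5.0% | 5.0% | 80% | 81% |
| 0.3 | 1.20 | 1.9% | 2.0% | 68% | 69% |
| 0.5 | 1.41 | 0.56% | 0.6% | 51% | 54% |
| 0.7 | 1.83 | 0.03% | 0.1% | 22% | 26% |

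The paired test had size 4.7% to 5.2% and power 80% to 81% throughout. At rho 0.3, 0.5 and 0.7 the unpaired power was 71%, 56% and 29% with n = 20, and 69%, 53% and 23% with n = 80. Repeat runs agreed within about 1 to 3 percentage points.

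**Women needed for 80% power, relative to a paired analysis:** ((1.96k + 0.84)/2.80)².
- rho 0.3: (3.18/2.80)² = 1.29
- rho 0.5: (3.61/2.80)² = 1.66
- rho 0.7: (4.42/2.80)² = 2.49

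**If demographics explain 10% of the variance:** k = sqrt(0.9/(1 - rho)), which is 1.13, 1.34 and 1.73 at the same rho. The loss shrinks but does not disappear.

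**One simulated data set** (n = 40, rho 0.5). With complete pairs every method estimates a change of -0.662. The SE is 0.197 stacked, 0.142 from a mixed model and 0.144 from a change score with two centred covariates (37 df). With 11 of the 40 post values missing, the estimates also differ: -0.660 stacked, -0.638 mixed model, -0.612 unadjusted change score on complete pairs. So the choice left open can affect the estimate as well as its precision.

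**The case against.** The strongest reply is that the plan is under-specified rather than wrong. It never says that rows are independent, and it does not define the dependent variable or the error term. An analysis of covariance on change scores fits the wording and would respect the pairing. The sphericity sentence is weak evidence, because sphericity is a restriction only with three or more time points; its absence from a two-point comparison shows little. *Standard* and *repeated measures* may simply distinguish two time points from all the weekly ones. Finally, the size of the loss rests on assumed rho and n, and with positive rho the error is conservative.

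Much of this stands. The intent may have been sound, the documents cannot say whether the loss is trivial or severe, and no false benefit arises when rho is positive. But the plan does name a method, and that method contains neither a subject effect, nor a change score, nor a baseline outcome value. Baseline levels are brought in only one sentence later, for two other analyses. An analyst who follows the text literally would run an unpaired comparison of paired data. Conservatism does not excuse that where this is the outcome's only analysis.

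**Conclusion.** The concern holds. As written, the pre/post analysis does not account for the pairing, and the eight questionnaires have nothing else. The consequence depends on rho. It is nil at zero; at 0.3 to 0.7, standard errors are 1.20 to 1.83 times too large and, with 40 women, 80% paired power falls to between 69% and 26%. At negative rho the test becomes anti-conservative (about 7% at rho = -0.2). These figures assume the literal reading, complete pairs, equal SDs and demographics that explain no variance; rho, n and the 80% reference power are not in the documents. This should be fixed before analysis. Confidence is medium, because a change-score analysis may have been intended.

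**What to change.** Replace the pre/post sentence with:

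> For each outcome, pre- and post-treatment values will be compared with a linear mixed model with time (pre, post) as a fixed effect, a within-woman covariance (subject random effect or unstructured) and baseline demographics as covariates. The mean within-woman change will be reported with its 95% CI.

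The unstructured option is the safer of the two, because a subject random effect cannot represent negative correlation.

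A change-score analysis with mean-centred covariates also respects the pairing and is acceptable. It is not identical: it adds time-by-covariate terms, changes the SE and degrees of freedom, and uses complete pairs only. If a change-score analysis of covariance was intended all along, the plan should say so.

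The cost is wording only, with no new data and no extra patients.

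### The primary pre/post ANCOVA takes its post-treatment mean only from women who return a post value, so this one-group study overstates benefit if women with a poor response stop early

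*Combined protocol and SAP*

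**What the plan says.** The document has no numbered sections. The relevant text is the paragraph on treatment and measures and the analysis paragraph that follows it.

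- **Design.** One treated group: "Consented subjects will then receive CBT-I treatment for 4 weeks (2 face-to-face sessions and 2 phone contacts"). No comparator or randomisation is described. The introduction also says that "another aim of this project is to test the acute and long-term efficacy of a single component behavioral therapy for menopausal-related insomnia", but no arm or between-group analysis for that therapy follows.
- **Primary comparison.** Every outcome "will be compared between pre and post-treatment (the primary evaluation time points) using standard analysis of covariance". The adjustment is for demographic characteristics. This covers both primary diary outcomes and all eight questionnaires.
- **Follow-on analysis.** Sleep efficiency and sleep latency, but not the questionnaires, are then modelled over the weekly points by repeated measures ANCOVA. For that model, "The repeated measures sphericity will be examined and an appropriate variance/covariance modeling structure will be used".
- **Data collected.** For the diary: "This diary will be collected at each visit". For the questionnaires: "The patients will fill out the following pre and post standardized surveys before and after the start of treatment", so they have no intermediate values.
- **Not stated.** The analysis population, the handling of a missing post-treatment value, any imputation and any sensitivity analysis. The paragraph shows no sign of redaction at this point.

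**The concern.** The reported effect is a change over time in one group. In a two-arm trial, similar dropout in both arms can partly cancel. Here nothing can offset it, so selective loss of women who are not improving goes directly into the estimate.

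The ANCOVA can be read in two ways:

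- **Change within woman.** A woman without a post value drops out altogether.
- **Time as a factor on all available rows.** Her pre value counts towards the pre mean, but the post mean still comes only from the women who remain.

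On both readings her intermediate diary weeks, which may show how she was responding before she stopped, play no part in the primary result. The claim that CBT-I improves sleep efficiency, latency and the questionnaire scores would then describe mainly the women who finished.

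**Working it through.** **Figure to reproduce.** There is none. The plan gives no sample size, SD, expected gain or dropout rate, so every numerical input below is an assumption.

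**Step 1: identity for the change-score reading.** Let d be the dropout proportion, and Dc and Dd the mean change in completers and dropouts.

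All-women mean = (1 − d) × Dc + d × Dd

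Bias of the completer mean = Dc − all-women mean = d × (Dc − Dd)

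With an assumed Dc of 10 sleep-efficiency points:

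| Dd | d = 10% | d = 20% | d = 30% |
|---|---|---|---|
| 10 | 0.0 | 0.0 | 0.0 |
| 5 | 0.5 | 1.0 | 1.5 |
| 0 | 1.0 | 2.0 | 3.0 |

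For example, with d = 20% and Dd = 0, the all-women mean is 0.8 × 10 + 0.2 × 0 = 8.0, reported as 10.

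**Step 2: simulation of both ANCOVA readings.** Assumed inputs: 100,000 women per scenario; baseline mean 75, between-woman SD 7; mean gain 8, SD 8, reached linearly over four weeks; weekly noise SD 4; dropouts observed to week 2. The likelihood estimate was obtained by regressing week 4 on weeks 0 to 2 in completers and predicting for all women, which is equivalent for this dropout pattern.

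| Dropout depends on | d | True | Change score | Time factor | Likelihood, weekly diaries | Zero change |
|---|---|---|---|---|---|---|
| Nothing | 20% | 8.02 | 8.01 | 8.01 | 8.03 | 6.41 |
| Early diary response | 10% | 8.02 | 9.31 | 8.88 | 8.02 | 8.38 |
| Early diary response | 20% | 8.06 | 10.39 | 9.59 | 8.05 | 8.31 |
| Early diary response | 30% | 8.03 | 11.31 | 10.19 | 8.01 | 7.92 |
| Unobserved change | 20% | 8.03 | 10.55 | 10.53 | 9.43 | 8.44 |

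At 20% dropout driven by early response, the overstatement is 10.39/8.06 = 1.29 for the change score and 9.59/8.06 = 1.19 for the time factor. The likelihood analysis removes it. When dropout follows the unobserved change itself, the likelihood analysis is still too large: 9.43/8.03 = 1.17.

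**Step 3: questionnaires.** With only two time points, a mixed model cannot condition on early response. A separate simulation assumed a true gain of 10, 19% dropout driven by early response, baseline SD 8, noise SD 5 and SD of gain 6 or 10. Completers gave 11.4 and 12.2; a two-point likelihood model gave 11.2 and 12.05. The share of bias remaining is 1.2/1.4 = 86% and 2.05/2.2 = 93%. Fitting the mixed model to the questionnaires alone is therefore not a remedy.

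**The case against.** The strongest reply is that the plan already calls for repeated measures modelling of all weekly points with a suitable covariance structure. That is compatible with a likelihood mixed model that keeps partial data, and assuming list-wise deletion is the least favourable reading. This stands as far as it goes: the text is ambiguous, and the weekly model could use the partial diaries. But it is the follow-on analysis, not the comparison marked as primary, and it leaves out the questionnaires.

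Four other objections stand and limit the point:

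- A reader might infer that the ANCOVA can use only women with a post value. The text does not say so; on the time-factor reading, women with only a pre value contribute to the pre mean. What holds on both readings is that the post mean excludes them.
- A reader might infer that the diaries of women who stop early are certainly available. The plan says only that diaries are collected at visits. It does not say how they are obtained at phone contacts or from women who stop.
- A reader might infer that a likelihood analysis restores the true value. That holds only when dropout depends on diary values actually collected.
- Every size shown is assumed, treatment lasts only 4 weeks, and neither sleep latency nor any individual questionnaire was simulated on its own scale.

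**Conclusion.** The point holds in conditional form. The stated primary analysis, in one group with no comparator, overstates benefit if women with a poor response stop early, and the plan contains nothing that would detect or limit this. The documents do not support saying that the study will overstate benefit: with dropout unrelated to response the bias is zero, and they give no dropout rate, SD or sample size from which to size it.

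On the assumed inputs in Step 2, dropout of 10% to 30% driven by early response inflates the sleep-efficiency gain by 16% to 41% on the change-score reading (9.31/8.02 to 11.31/8.03) and by 11% to 27% on the time-factor reading (8.88/8.02 to 10.19/8.03). These figures illustrate direction and order of size; they do not predict this study's result.

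For sleep efficiency and latency this is more than missing detail, because a better method is available using data the plan already collects. For the questionnaires the remedy is weaker and depends on how well the diaries predict the missing scores.

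**What to change.** 1. **Sleep efficiency and sleep latency.** Take the primary post-minus-pre estimate from one likelihood-based repeated measures mixed model per outcome. Include all women who start CBT-I and every available diary value. Keep the pre-treatment value as an outcome time point (so not also as a covariate), treat time as categorical and retain the planned demographic covariates. Use an unstructured covariance, with a simpler structure named in advance in case it does not converge.
2. **Questionnaires.** Use multiple imputation of the post score, with the baseline score and the available weekly diary values in the imputation model.
3. **All outcomes.** Report how many women contribute a post value. Add a sensitivity analysis giving zero change to women without one, because the mixed model and the imputation both remain biased if dropout depends on unobserved change. Do not present it as a lower bound: in Step 2 it came out above the truth (8.31 against 8.06) where the simulated dropouts had worsened on average, since (8.06 − 8.31)/0.2 = −1.25.

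The cost is SAP wording and a little more analysis work, with no new patients or data. Provided completers improve on average, the sensitivity estimate will be less favourable than the completer result, since it equals (1 − d) × Dc.

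### The weekly model of sleep efficiency and sleep latency adjusts for time since cancer, a covariate that does not fit the stated menopausal-insomnia population and has no coding rule

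*Combined protocol and SAP*

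**What the plan says.** The document has no numbered sections, so places are named here by content.

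- **Background and aims.** Menopausal insomnia is the subject throughout. The plan says that "the efficacy of cognitive behavioral therapy for insomnia comorbid with menopause, one of the primary focuses of the present proposal, has not been tested", and its final aim is to "determine the efficacy of CBT-I on these measures in women with menopausal-related insomnia".
- **Enrolment and procedures paragraph.** Those approached are described as "Each patient who meets the criteria and opts for CBT-I as part of their standard clinical treatment for insomnia". The criteria themselves are not in the supplied text.
- **Statistical analysis paragraph, first analysis.** Each outcome is to be "compared between pre and post-treatment (the primary evaluation time points) using standard analysis of covariance, with the baseline demographics as covariates". No cancer variable is named.
- **Statistical analysis paragraph, second analysis.** "Then the data on sleep efficiency, sleep latency, will be analyzed across all of the weekly time points using repeated measures analysis of covariance". This model adjusts for where each woman started on the two outcomes and, in the plan's words, "along with age, BMI, and time since cancer development". On the target of inference, the plan states: "The repeated measures modeling will primarily evaluate the main time effect".

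The second analysis contains the only mention of cancer in the document. The plan does not define the covariate, assign a value to women without cancer, or give a rule for missing covariates.

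**The concern.** Time since cancer is a number only for someone who has had cancer. In the population that the background describes, some or all of the women may have no such value. The analyst must then make a choice that the plan does not make: fit complete cases, drop the term, or assign a code such as 0. These choices differ in who is analysed and, under some model forms, in what the time effect means.

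The outcomes concerned are the two named in the primary aim, and the weekly model is where their course over treatment is estimated. With no stated rule, the handling would be settled after the data are collected, and a reader could not tell whether it was chosen with results in view.

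**Working it through.** **1. The text.** The plan gives no sample size, power or effect size, so there is no figure to reproduce. Side by side, the background describes menopausal insomnia with no reference to cancer, while the weekly model requires a cancer date for each woman. Either the covariate is wrong for this population, or the population statement omits a cancer history that was intended. The two cannot both be complete as written.

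**2. Inputs for a sense of size.** None of these is in the supplied text; all are assumptions.
- Share with a cancer history: c = 0% to 100%.
- Sample size: N = 100 (50 and 200 also tried).
- Four weekly values, with the time effect taken as week 4 minus week 1.
- SD of that change: 8 points.
- Time since cancer: uniform on 1 to 10 years in women with a history (used in step 4 only).

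**3. Complete-case fit.** The number kept is n = N × c. In an additive model the standard error of the contrast is about 8/√n. That is 8/√100 = 0.80 with everyone, so the ratio to the full sample is 1/√c. If covariate-by-time terms are fitted, each contrast has five parameters (intercept, one baseline level, age, BMI, cancer time), and the residual df are N × c − 5. The last column was simulated with 1,000 data sets per cell, against a fit of all women without the term.

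| c | Women kept of 100 | SE ratio, additive (1/√c) | Residual df, covariate-by-time | SE ratio, covariate-by-time |
|---|---|---|---|---|
| 0% | 0 | no fit | none | no fit |
| 5% | 5 | 4.47 | 0 | not estimable |
| 10% | 10 | 3.16 | 5 | 3.0 |
| 20% | 20 | 2.24 | 15 | 2.2 |
| 50% | 50 | 1.41 | 45 | 1.4 |
| 100% | 100 | 1.00 | 95 | 1.0 |

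Simulated ratios for the additive model were 4.42, 3.13, 2.24, 1.41 and 1.00 at c = 5, 10, 20, 50 and 100%, in line with the formula. If both baseline levels enter each model, every df figure falls by one.

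**4. Coding women without cancer as 0.** At c = 0% the covariate is constant and its coefficient cannot be estimated. Between 0% and 100% everyone is kept, but the code for no cancer cannot be told apart from a very recent cancer.
- Additive model with balanced data, or mean-centred covariate: the time contrast does not change.
- Covariate-by-time terms with cancer time uncentred: the contrast refers to a woman with cancer time 0, so it moves by the estimated slope times the mean of the covariate.

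For the second case, take a true slope of zero and the other covariates centred. The mean of the covariate is 5.5c. Its variance is 37c − 30.25c², where 37 = 6.75 + 30.25 is the mean square of a uniform on 1 to 10. The SD of the shift is then 0.80 × 5.5c/√(37c − 30.25c²), and the mean absolute shift is about 0.80 times that SD (the factor √(2/π)).

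| c | SD of shift | Mean absolute shift, formula | Mean absolute shift, simulated | 95th percentile, simulated |
|---|---|---|---|---|
| 5% | 0.17 | 0.13 | 0.14 | 0.33 |
| 10% | 0.24 | 0.19 | 0.19 | 0.50 |
| 20% | 0.35 | 0.28 | 0.29 | 0.70 |

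Against the standard error of 0.80, the simulated mean shifts are 0.14/0.80 = 0.18, 0.19/0.80 = 0.24 and 0.29/0.80 = 0.36 of one standard error. For the same three shares, the mean shifts were 0.19, 0.28 and 0.43 points at N = 50, and 0.09, 0.13 and 0.20 at N = 200.

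**5. Reading the two branches.** The loss of women under a complete-case fit is the serious consequence. The shift from 0-coding is modest and depends on a model form that the plan does not state.

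**The case against.** The strongest case against giving this weight has four parts.

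- **It is a follow-on model.** The pre/post comparison is at the primary time points and does not name the term. This stands, and it limits the finding to the weekly analysis.
- **The harm is hypothetical.** The plan does not prescribe complete cases, and if no participant has a cancer history the fit fails visibly and the term would be dropped. The plan speaks of a main time effect and mentions no covariate-by-time terms. In a balanced additive model a covariate that is fixed within each woman leaves the contrast alone, provided everyone is kept. All of that is correct. But the model form and the handling are both unstated, so keeping everyone is itself an unrecorded decision, and dropping the term is a departure from the plan.
- **The 0-coding shift is small and not specific to this covariate.** It is well under one standard error on average, and uncentred baseline, age and BMI would move the same contrast far more: about 9 points on average, assuming age 55 (SD 5), BMI 28 (SD 5) and baseline efficiency 75 (SD 10). This also stands. Centring is a general matter that deleting the phrase would not settle, so the case should not rest on the 0-coding figures.
- **The mismatch may lie elsewhere.** The eligibility criteria are not in the supplied text, and the enrolment and analysis paragraphs speak only of patients and subjects, never of women or menopause. A cancer-history requirement cannot be ruled out. If there is one, the covariate is defined for everyone, but the title and aims then misdescribe the population. A correction is needed either way.

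**Conclusion.** The concern holds and should be fixed before analysis. As written, the weekly model of the two primary-aim sleep outcomes contains a covariate that does not match the stated population, has no value for a woman without a cancer history, and carries no coding rule. This follows from the text alone and needs none of the assumed figures.

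The size cannot be fixed from the document. Under a complete-case fit it ranges from no model at all (no woman with a cancer history), through standard errors about 3.2 and 2.2 times larger at shares of 10% and 20%, to no loss if every woman has one. The ratio 1/√c does not depend on the assumed N or SD. Other handling could leave the time effect unchanged, but the plan does not choose it. The pre/post analysis is not implicated.

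**What to change.** Decide which statement is right and record the decision, dated, before the weekly analysis is run.

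- **If the population is as the background states:** delete the time-since-cancer term. The covariates are then the baseline outcome levels, age and BMI. This removes one phrase and needs no new data, visits or participants.
- **If women with a cancer history were intended:** correct the population statement and define the covariate for every participant. The definition should give the event from which time is counted, the coding for anyone without a history, and the centring. This costs one corrected statement and one coding rule.

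In either case, state whether covariate-by-time terms are fitted and, if so, that all covariates are mean-centred. The time effect then has one meaning.
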